IGNITE

A Randomized Controlled Trial of Concentrated Investment in Black Neighborhoods to Address Structural Racism as a Fundamental Cause of Poor Health

Study Protocol

May 2023

Outline

- 1. Abstract
- 2. Overall objectives
- 3. Aims
 - 3.1 Primary outcome
 - 3.2 Secondary outcomes
- 4. Background
- 5. Study design
 - 5.1 Design
 - 5.2 Study duration
 - 5.3 Target population
 - 5.4 Accrual
 - 5.5 Key inclusion criteria
 - 5.6 Key exclusion criteria
- 6. Subject recruitment
- 7. Subject compensation
- 8. Study procedures
 - 8.1 Consent
 - 8.2 Procedures
- 9. Analysis plan
- 10. Investigators
- 11. Human research protection
 - 11.1 Data confidentiality
 - 11.2 Subject confidentiality
 - 11.3 Subject privacy
 - 11.4 Data disclosure
 - 11.5 Data safety and monitoring
 - 11.6 Risk/benefit
 - 11.6.1 Potential study risks
 - 11.6.2 Potential study benefits
 - 11.6.3 Risk/benefit assessment

12. Bibliography

1. Abstract

Black Americans in the US fare worse across nearly every health indicator compared to White individuals. In Philadelphia, the location of this study, these health disparities culminate in a stark longevity gap, with average life expectancies in poor, predominantly Black neighborhoods being 20 years lower than in nearby affluent, predominantly White neighborhoods. We will conduct a cluster randomized controlled trial (RCT) of a suite of place-based and financial-wellbeing interventions at the community, organization, and individual/household levels that address the social determinants of racial health disparities. At the community level, we address underinvestment in Black neighborhoods by implementing vacant lot greening, abandoned house remediation, tree planting, and trash cleanup. At the organizational infrastructure to increase reach and maximize efficiency. At the individual/household levels, we increase access to public benefits, financial counseling and tax preparation services, and emergency cash assistance. We will test this "big push" intervention in 60 Black neighborhood microclusters, with a total of at least 480 adults and 480 children across up to 720 households. We hypothesize that this "big push" intervention will have significant impact on overall health and wellbeing.

2. Overall objectives

The objective is to develop and test a concentrated suite of place-based and financial well-being interventions at the community, organization, and individual levels to address structurally-mediated racial health disparities.

3. Aims

3.1 Primary outcomes

Overall health and psychological distress of participants.

3.2 Secondary outcomes

The secondary outcomes are described in detail in Table 1 below.

4. Background

Black individuals in the United States fare worse than White individuals across almost every social, economic, and health indicator. The Black health disadvantage starts at birth, reflecting the cumulative toll of racialized social stressors and healthcare discrimination on maternal health and resulting in higher rates of preterm birth and low birth weight. Black youth are disproportionately exposed to environmental toxins such as lead and adverse childhood events such as financial hardship and neighborhood violence. Black adults have higher rates of chronic disease, including diabetes, hypertension, as well as many cancers. These and other forces culminate in a stark racial longevity gap: in Philadelphia, the location of this study, life expectancy for people living in a poor, predominantly Black neighborhood is 20 years lower than for people living in a nearby affluent, predominantly White neighborhood.

The fundamental cause of these striking and pervasive disparities is structural racism – the confluence of deep historical, institutional, cultural, and ideological forces that unequally distribute resources and risks across racialized groups⁻ Structural racism patterns health by affecting a range of interconnected, mutually reinforcing social determinants of health at the national, neighborhood, household, and individual levels. Most notably, longstanding, systematic disinvestment has resulted in highly segregated Black neighborhoods with dilapidated

environmental conditions and severe economic insecurity within Black households, leading to a "feedback loop of concentrated racial disadvantage," all of which have been strongly tied to poor health.

Most interventions seeking to address racial health disparities focus on individual-level behaviors and outcomes, or individual channels by which structural racism harms health. However, by failing to address upstream social determinants, these interventions have had limited population level impact. A multi-level, multi-component intervention package focused on a range of social determinants of health is necessary to meaningfully address structural racism as a fundamental cause of racial health disparities.

5. Study design

5.1 Design

This is a cluster randomized controlled trial. We will enroll 60 neighborhood microclusters in the study. Half of the study clusters will be randomized to the intervention and the other half to the control group.

5.2 Study duration

The study is expected to begin in September 2022 and participants will continue in the study for 24 months. The study will last for 5 years. Year 1 will include protocol development and cluster selection. Participant selection and baseline data collection will start in Year 2 and last 9 months. The place-based and financial well-being interventions will begin quarter 3 of Year 2 and last 18 months, followed by follow-up data collection. Qualitative interviews will be conducted in Year 3. Data analysis occurs from Year 2 into Year 5. Year 5 will involve final data analysis, manuscript preparation and submission, and dissemination of study findings.

5.3 Target population

Our population will include adults living in our target Philadelphia neighborhood microclusters.

5.4 Accrual

We will enroll at least 480, and up to 720, adults from 60 neighborhood microclusters in the study, half of which will be randomized to the intervention and half to the control. If more than one household resident is interested and eligible in the study, the person with the most recent birthday will be enrolled. One participant per household is eligible.

If there are one or more children ages 3-17 living in the household, this child's caregiver will also be given the option of completing an additional survey regarding their child's health. We will enroll adult caregivers of 480 children ages 3-17, including the 480 adults described above and up to 240 additional participants.

5.5 Key inclusion criteria

To be eligible patients must:

- 1. Be at least 18 years of age
- 2. Have the ability to communicate via text messaging
- 3. Be comfortable communicating in English
- 4. Be a permanent resident of the home where they are to be enrolled
- 5. Have knowledge of their household finances

5.6 Key exclusion criteria

- 1. Individuals who plan to move out of the study microcluster within 6 months
- 2. Individuals who are unable to fully consent and participate based on CC team assessment

5.7 Key inclusion criteria for IGNITE Kids Caregivers

To be eligible caregivers must:

- 1. Be at least 18 years of age
- 2. Be the primary caregiver of one or more children ages 3-17 years
- 3. Have the ability to communicate via text messaging
- 4. Be comfortable communicating in English
- 5. Be a permanent resident of the home where they are to be enrolled
- 6. Have knowledge of their household finances

5.6 Key exclusion criteria

- 1. Individuals who plan to move out of the study microcluster within 6 months
- 2. Individuals who are unable to fully consent and participate based on CC team assessment
- 3. Individuals who are not the primary caregivers of children ages 3-17 years

6. Subject recruitment

Participant recruitment will commence in September 2022 and will run through March 2024. Recruitment in control and intervention microclusters will occur simultaneously. The data analyst who performed the randomization will randomize microcluster order (stratified by intervention and control status and city section) to determine the order in which recruitment occurs.

Several Community Coordinator (CC) teams will be recruiting participants. A given team of two will remain in a microcluster until a total of 12 participants are fully enrolled in that microcluster. They will then move to the next microcluster on the randomly generated list. Multiple microclusters will be undergoing enrollment simultaneously. The CC team will be blinded to what arm of the trial the microcluster is in until all participants are enrolled. Participants will also be blinded until after everyone in that cluster is enrolled.

When starting recruitment in a new microcluster, the CC team will first place door knockers on all homes within the microcluster boundaries to alert neighbors to the presence of the study team in the neighborhood. They will then begin door-to-door recruitment at a pre-determined house that is closest to the geographic center of the study microcluster. They will follow a pre-determined route throughout the neighborhood that includes walking up one side of the street and back down the other side of the street before moving on to an adjacent block, and the next adjacent block, etc. The block order will be pre-determined by the data analyst performing randomization to where blocks will be ordered as closet to concentrically in a clockwise manner from the first block.

If more than one household resident is interested and eligible in the study, the person with the most recent birthday will be enrolled. One participant per household is eligible. The CC team will conduct an informed consent with all participants. The CC team will then administer a demographic and baseline survey and directly enter data into REDCap. If the resident is interested in the study but is not available or able to complete the baseline survey at the time of the first encounter, CC team will conduct the Informed Consent Process (resident will sign the Informed Consent Form) and then identify a time to reschedule complete the baseline survey. If necessary, the CC team can schedule to meet with the resident virtually to complete the baseline survey.

Completion of the baseline survey indicates resident is fully enrolled in the study and is to be considered the official date of enrollment.

If there are one or more children ages 3-17 living in the household, the child or children's primary caregiver will be given the option of completing an additional follow-up survey regarding their child's health and wellbeing. One participant per household is eligible to complete the children's health and well-being survey for up to three children residing in the household. If more than three children ages 3-17 reside in the household, the enrolled caregiver will be asked to complete the survey for the three children with the most recent birthdays. We will enroll adult caregivers of approximately 480 children ages 3-17. To meet this goal, approximately up to 240 additional caregivers will be enrolled. Towards this end, after enrollment of adult subjects is complete within a microcluster, CC teams will continue to enroll caregivers from homes within a microcluster with which contact has not already been made. Enrollment will end when either enough caregivers are enrolled for up to 10 children per microcluster or two weeks after adult enrollment closes within the microcluster.

Subject compensation

Participants will be compensated \$40 after the baseline survey using ClinCards, \$15 after a 6 month check in, \$15 after a 12 month check in, \$15 after an 18 month check in, and \$40 after a follow up survey. Participants with children who agree to complete a supplemental follow-up survey regarding their children's health will receive an additional \$20 per child (up to 3 children per household). Follow up data collection will occur between September 2024 and March 2025, with each participant surveyed 24 months after their initial enrollment date. If participants are selected to participate in an additional qualitative feedback interview, they will receive \$40 compensation.

8. Study procedures

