Within the city section strata, we conducted a covariate-constrained randomization process in order to ensure balance between microclusters randomized to intervention and those randomized to control based on relevant sociodemographic variables. Covariate-constrained randomization quantifies baseline imbalance of microcluster-level covariates (both categorical and continuous) across all microclusters using a balance metric and then randomly selects one randomization schema from those with acceptable balance. Furthermore, the intraclass correlation coefficient calculation – a measure of reliability – remains unaffected under a constrained randomization model.²

We chose the following covariates to balance on: age (categorized by shares under age 19, 19-49, 50-64, and 65 and above); gender; median income; unemployment rate; amount of vacancy; and tree canopy. We did not balance on race/ethnicity (e.g., % Black) or poverty rates, since initial criteria for study site selection focused on census tracts whose populations were at least 80% Black and with elevated poverty rates. The covariates were measured based on their distribution of means by each microcluster using block group data from the US Census Bureau's 2020 ACS. Each microcluster's mean is the weighted mean for the covariates based on percent of land area in each census block group in which the microcluster sits. A microcluster could be in one census block group or could cross over 2 or 3 census block groups. Following the literature, we used a threshold of 0.2 for standardized mean differences in the covariates.

We used the -cvcrand- package, specifically the -cvrall- function, in R to calculate the final covariate balance metric and selection schema at random after covariate balance by cluster was achieved.²

Enrollment

Participant recruitment will commence in September 2023 and will run through May 2023 (or until we enroll at least 480, but no more than 720, in the main trial). Recruitment in control and intervention microclusters will occur simultaneously. The data analyst who performed the randomization will randomize microcluster order (stratified by intervention and control status and city section) to determine the order in which recruitment occurs.

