If more than one household resident is interested and eligible in the study, the person with the most recent birthday will be enrolled. One participant per household is eligible. The CC team will conduct an informed consent with all participants. The CC team will then administer a demographic and baseline survey and directly enter data into REDCap. Participants will be compensated \$40 after the baseline survey using ClinCards, \$15 after a 6 month check in, \$15 after a 12 month check in, \$15 after an 18 month check in, and \$40 after a follow up survey. Follow up data collection will occur between September 2024 and March 2025, with each participant surveyed roughly 24 months after their initial enrollment date.

For all households including one or more children ages 3-17 living in the household, the child or children's primary caregiver will be asked to complete an additional follow-up survey regarding their child's health and well-being, for up to three children per household. If more than three children ages 3-17 reside in the household, the enrolled caregiver will be asked to complete the survey for the three children with the most recent birthdays. Participants who complete the follow-up survey regarding children's health will be compensated \$20 after survey completion.

To support recruitment efforts, we will partner with community organizations to widen the reach of study promotion and to improve dissemination of recruitment materials, particularly in communities where recruitment is found to be difficult. We will also use a community-facing website to promote the study and increase screening for enrollment.

Respondent Driven Sampling

IGNITE referrals. Respondent driven sampling will be implemented to drive enrollment when Community Coordinators identify that completing enrollment (i.e., reaching at least 8 participants) is difficult in a particular microcluster. This strategy will be implemented only as a contingency.

Participants will then be invited to refer individuals who they think may be willing to participate in the study. If those referrals meet eligibility criteria and are successfully enrolled, the participant who made the initial referral will receive a payment of \$10 via their ClinCard for that successful referral.

Participants can make an unlimited number of referrals, but only up to 2 referrals will be enrolled per participant (to limit referral networks at a max of four networks per cluster.)

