IGNITE Kids referrals. To support enrollment efforts for the IGNITE Kids sub study, participants may also be asked if they know of and are willing to connect the study team to any families in their neighborhood with children ages 3-17. Participants will be compensated \$10 for successful referrals. Referrals for IGNITE Kids will count towards the 2-referral limit described above.

Tree referrals. To support efforts in planting at least 10 trees in each intervention microcluster, participants will be invited to refer neighbors who may be willing to receive free trees through the study. Referrals may be accepted at the time of enrollment and/or during subsequent home visit(s). Participants will be compensated \$10 for successful referrals. Participants can make and be paid for an unlimited number of tree referrals or for the amount needed until tree planting goals have been met in their particular microluster.

Intervention

Place-Based Interventions

Our suite of place-based interventions consists of four separate interventions which will all be performed simultaneously in all of the intervention microclusters. The four interventions are: vacant lot greening, tree planting, weekly trash pickup, and abandoned house remediation. The first three will be performed through the Pennsylvania Horticultural Society (PHS), while the last will be performed through the City of Philadelphia.

After microclusters have been selected and randomized to the intervention arm (n=30), we will conduct an inventory of the locations of existing vacant lots, abandoned houses, and tree canopy. All place-based interventions will start in April 2023. See below for protocol for each intervention including the intervention timeframe for each.

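### Recruitment, intervention and follow-up dates cannot all hold, and Section 9 starts the difference-in-differences intervention period at the end of enrolment instead of at the start of place-based work

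*Combined protocol and SAP*

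**What the plan says.** **Recruitment.** Section 6: "Participant recruitment will commence in September 2022 and will run through March 2024". Section 8.2 (Enrollment): "Participant recruitment will commence in September 2023 and will run through May 2023". Section 5.2: "Participant selection and baseline data collection will start in Year 2 and last 9 months".

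**Start of work.** Section 5.2: "The place-based and financial well-being interventions will begin quarter 3 of Year 2 and last 18 months, followed by follow-up data collection". Section 8.2 (Place-Based Interventions): "All place-based interventions will start in April 2023", with four components "which will all be performed simultaneously in all of the intervention microclusters". The component paragraphs give April to June 2023 for greening, April 2023 to August 2024 for trash cleanup, April to August 2023 for house remediation, and September to October 2023 for trees. Only the siting of trees is made conditional on the microcluster being fully enrolled.

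**Follow-up.** Section 7: "Follow up data collection will occur between September 2024 and March 2025, with each participant surveyed 24 months after their initial enrollment date". Section 8.2 repeats the window, "with each participant surveyed roughly 24 months after their initial enrollment date".

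**Analysis.** Completing the baseline survey defines enrolment (Section 6), and every main GEE model adjusts for the baseline outcome (Section 9). For microcluster-level outcomes, Section 9 uses 8 quarters before the intervention, then an intervention period from the end of enrolment and baseline collection to the start of follow-up, then a post period equal to the follow-up window. The post-period term is named as the effect of interest. Tables 1 and 2 give the quarterly data as 8 quarters before enrolment and 4 quarters after the intervention period.

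**The concern.** Two things depend on which calendar governs.

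First, if recruitment is still open when visible work begins, some baselines in intervention microclusters may already reflect the place-based treatment. Adjusting for such a baseline tends to pull the estimate towards the null. Visible work also puts at risk the promise in Sections 6 and 8.2 that coordinators and participants stay blinded until the microcluster is full.

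Second, Section 9 ties the intervention period to the end of enrolment and never refers to the start of work. If enrolment ends well after April 2023, treated quarters may sit in the reference period of the two-term model and dilute the post-period effect. In the event-study model they would enter the parallel-trends check. The analyst would have to choose the period boundaries, possibly after seeing data.

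**Working it through.** **1. Calendars.** Inputs are the dates above. Implied enrolment is the follow-up window minus 24 months: September 2024 to March 2025 becomes September 2022 to March 2023.

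| Source | Enrolment window | Months | On or after April 2023 | 24-month visits inside the follow-up window |
|---|---|---|---|---|
| Section 7, minus 24 months | Sep 2022–Mar 2023 | 7 | 0 | 7 of 7 |
| Section 6 | Sep 2022–Mar 2024 | 19 | 12 | 7 of 19 |
| Section 8.2 as printed | Sep 2023–May 2023 | impossible | – | – |
| Section 8.2, start year read as 2022 | Sep 2022–May 2023 | 9 | 2 | 7 of 9 |
| Section 8.2, end year read as 2024 | Sep 2023–May 2024 | 9 | 9 | 0 of 9 |

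On Section 6's dates a March 2024 enrollee has at most 12 months of follow-up when the window closes in March 2025.

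Section 5.2 is in study years. If baseline opens Year 2, it fills months 1–9. Work starts in quarter 3, that is month 7, 8 or 9, so 3, 2 or 1 whole months overlap by its own schedule. If Year 2 opens in September 2022, work starts in March–May 2023, consistent with April 2023. If Year 1 opens in September 2022, the stated study start, work starts in March–May 2024, about a year later than Section 8.2 says.

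**2. Period lengths on Section 6's dates.** Work by trash-cleanup dates: April 2023 to August 2024 = 17 months. Section 9's intervention period: April to August 2024 = 5 months. The other 17 − 5 = 12 months (Q2 2023 to Q1 2024, four quarters) come before it.

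**3. Effect on the two-term model.** Assume the same true rate ratio R in every treated quarter and level underlying rates. With t treated quarters among 8 reference quarters, the reference ratio is (8 − t + tR)/8, and the post-period estimate is R divided by that.

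- Pre-quarters counted back from Section 9's own period start (Q2 2024): t = 4. For R = 0.80 the reference ratio is (4 + 3.2)/8 = 0.90 and the estimate is 0.80/0.90 = 0.89. Share of log effect kept: ln 0.889/ln 0.80 = 0.53. For R = 0.70, 0.70/0.85 = 0.82; for R = 0.90, 0.90/0.95 = 0.95.
- Pre-quarters counted back from April 2023: t = 0 and 0.80 is recovered. The four quarters belong to no listed period, so they leave the analysis.
- Enrolment closing by March 2023, or by May 2023 with Q2 2023 coded as intervention: t = 0, estimate 0.80. If Q2 2023 is coded as pre-intervention instead, t = 1 and the estimate is 0.80/0.975 = 0.82.

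The values of R are illustrative; none is in the documents.

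**4. Primary outcomes, illustration only.** Proportion of effect lost ≈ baseline slope × share of baselines that are late × fraction of the effect already present. Assume a slope of 0.5–0.7, 10–50% of the effect present, and even accrual. The 2-of-9 calendar then gives 0.5 × 0.222 × 0.1 = 0.011 to 0.7 × 0.222 × 0.5 = 0.078, or about 1% to 8%. It scales with the late share. Slope, fraction and accrual pattern are assumptions.

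**The case against.** The strongest reply is that one calendar fits most of the plan: enrolment September 2022 to March 2023, work April 2023 to August 2024, follow-up September 2024 to March 2025. On it, the end of enrolment is the start of work and Section 9 does no harm. The tree paragraph also argues against the late calendars: siting waits until an intervention microcluster is full, yet planting is dated September–October 2023. This stands as a limit on the likely harm. It does not show which calendar governs, and Sections 5.2, 6 and 8.2 do not fit it.

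Four stronger readings are tempting and are not supported.

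- A reader might count the four unassigned quarters as reference quarters, and so infer dilution on Section 6's dates under any anchor. Section 9 limits the analysis to three listed periods, so those quarters drop out and nothing is diluted.
- A reader might take the timeframes in Tables 1 and 2 as contradicting Section 9. They may only describe a wider data extract.
- A reader might infer that all work began in every intervention microcluster in April 2023. Greening and remediation have windows, not start dates per microcluster, and trees come later. Only weekly cleanup is clearly continuous from April.
- A reader might conclude that the primary result is biased. April–May 2023 baselines would use 30-day recall for distress and limited days, and a longer look-back for health change, so much of what they measure precedes the work.

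It is also fair that the difference-in-differences outcomes are secondary, that the planned detrending is a specification test, and that quarter-specific event-study coefficients remain estimable.

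**Conclusion.** This is an internal inconsistency that should be fixed. Confidence is high that the dates conflict and that Section 9's intervention period is tied to enrolment instead of to the work. Confidence is low about the size of any bias.

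On Section 6's dates, the secondary post-period effect runs from undiluted to about half the log effect lost (0.80 estimated as 0.80 to 0.89), depending on an anchor the text leaves open. The upper end needs a March 2024 close and a constant effect from the first treated quarter. There is no loss if enrolment closed by March 2023, or by May 2023 with Q2 2023 coded as intervention; Section 9 states neither.

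For the primary outcomes, overlap is possible but not shown. Its effect cannot be sized from the documents and is probably small if enrolment closes by May 2023.

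**What to change.** 1. Reconcile Sections 5.2, 6, 7 and 8.2 (Enrollment, Place-Based Interventions, Tree planting) to one calendar. The documents do not show which dates are right, and this review does not presume it.
2. In Section 9, define the pre-period as the 8 quarters ending before the quarter in which place-based work begins. Run the intervention period from that quarter, inclusive, to the end of the intervention. State one post period, and align the Table 1 and Table 2 timeframes with it. If the present August/September 2024 boundary stays, say which period Q3 2024 belongs to.
3. Leave the primary model unchanged. Report by arm how many baselines were collected before and after work began. Only if some are late, add a sensitivity analysis restricted to participants enrolled before work began.

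The cost is protocol wording and a few lines of code, with no loss of precision in the primary analysis. The restricted analysis is less precise and may drop whole microclusters. Under even accrual it would keep about 480 × 7/9 = 373 participants on the 2-of-9 calendar, or 480 × 7/19 = 177 on Section 6's dates. It is not needed if no baseline is late.
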